### **CASE DEFINITIONS for COVID-19:**

Confirmed COVID-19 case: A participant will be considered COVID-19-positive if he/she has a valid positive result on a country-approved RT-PCR test.

No COVID-19: Participants will be considered COVID-19-negative if they have a valid negative RT-PCR result.

The respiratory sample for the **index test** (molecular POC) will be processed by personnel trained by the test manufacturer directly, or FIND team trained by the manufacturer, following the specific IFU provided by the manufacturer. The result will be recorded in the corresponding CRF. After assay completion, the test report generated by the device will be exported and uploaded in Open Clinica and a copy filed in the Investigator Site File (ISF) either paper or electronic. In case the test report cannot be exported from the device, a screenshot/picture of the test screen will be uploaded

in OpenClinica as source document for this study and a copy filed in the Investigator Site File (ISF) either paper or electronic. The molecular POC device will be operated, cleaned and maintained only by trained staff and according to manufacturer's instructions, ensuring device technical and health checks will be performed, where necessary.

Enrolled participants can be diagnosed based on RT-PCR results and clinical signs and symptoms by their treating physician; *the results of the molecular POC tests will not be used for clinical management.*

### **6.3 Other Tests: COVID-19 Genome Sequencing**

Leftover aliquot of nasopharyngeal swabs tested positive in the reference assay will undergo sequencing for surveillance of SARS-CoV-2 variants for study purposes. Sequencing will be performed following the procedure established in the sequencing laboratory/facility routinely utilized by the selected study sites. (SITE to add specific details on their sequencing facility and procedure).

### **6.4 Safety Assessments**

The study will comply with all biosafety precautions appropriate to the study procedures, including respiratory specimen collection, handling, processing, and disposal, to protect study participants and personnel. The index test will be performed within designated SARS-CoV-2 isolation zones. The reference test will be performed in laboratories designated for safe handling of these specimen types and following laboratory's safety protocols. All testing will be performed by appropriately trained personnel wearing all required PPE. The probability of (serious) adverse events (AE, SAE) occurring to a study participant while collecting the respiratory sample is deemed to be extremely low, as this procedure is considered to be very low risk. Nevertheless, should such event occur, this will be managed following the procedures described in section 7.

### **6.5 Other Study Procedures**

The operators of the molecular POC device will be asked to complete an Ease-of-Use questionnaire to assess the perceived usability of index test. The answers provided by the operators will be converted into a score using a System Usability Scale.

## **7 Safety and Incident Reporting**

Given that this is a diagnostic accuracy study that is not utilizing test results for patient care in clinical decision making and given that additional procedures for the study, i.e., respiratory swabs collection are extremely low risk, the probability of an AE or SAE occurring to a study participant to be associated with the investigational products is extremely low. There are no known expected

participant's reactions beyond mild discomfort. Nevertheless, safety and incident reporting are described in specific sections below. Warnings, precautions, and safety recommendations described in each device IFU provided by the manufacturer will be carefully read and observed. Country-specific safety reporting requirements to IEC/IRB and Regulatory Authorities will be followed.

This study does not have predefined termination criteria being an accuracy study.

**SITE to add details on specific safety reporting requirements by the IEC/IRB**

## 7.1 Adverse Events and Serious Adverse Events

The definitions of an Adverse Event (AE) and Serious Adverse Event (SAE) can be found in Appendix 2.

Given the nature of this study AE reporting is limited in scope to:

- SAEs that may be associated with respiratory sample collection.
- SAEs that occur at the testing sites using the investigational product (see section 7.1.3 Medical device incidents).
- Any other serious events that affect the rights safety or welfare of subjects.

There is minimal to absent likelihood of AEs for the current protocol evaluating an external *in vitro* medical diagnostic device for both study participants and devices users. For study participant, the AE will not be associated with the diagnostic device itself but could be associated with the performance of the respiratory sample collection procedure (procedure-related AE).

### 7.1.1 Time Period for Collecting SAE Information

Information will be collected during specimen collection and testing of the investigational product. SAEs will be recorded and reported to the sponsor or designee within 24 hours of the Investigator aware of the event.

All participant-related SAEs will be collected from the signing of the informed consent form (ICF) until completion of the procedures to collect the respiratory specimens and participant discharged from the study.

All device operator-related SAEs will be collected during all steps required for running the assay and during cleaning/maintenance procedures performance, during all periods of the study in which the device is used.

The Investigator will submit any updated SAE data to the sponsor within 24 hours of being made aware of the event.

Investigators are not obligated to actively seek SAEs after conclusion of the study participation. However, if the Investigator learns of any SAE, including a death, at any time after a participant has been discharged from the study, and he/she considers the event to be reasonably related to the study participation, the Investigator must promptly notify FIND.

### **7.1.2 Reporting and follow up of SAEs**

All SAEs will be followed until resolution, stabilization, or the event is otherwise explained. Prompt notification by the Investigator to FIND study team (Clinical Study Manager and/or Clinical Research Associate, Scientist and Project Manager) of a SAE is essential so that legal obligations and ethical responsibilities towards the safety of participants and operators are met. Each site will also be provided with AE log and SAE report form. SAEs will be reported to the sponsor or designee within 24 hours of the Investigator aware of the event.

FIND will comply with country-specific regulatory requirements relating to safety reporting to the regulatory authority, Institutional Review Boards (IRB)/Independent Ethics Committees (IEC), and investigators.

An Investigator who receives a safety report describing a SAE or other specific safety information (e.g., summary or listing of SAEs) from FIND will review and then file it in the Investigator Site File (ISF) and will notify the IRB/IEC, if appropriate, according to local requirements.

### **7.1.3 Medical Device Incidents (including Malfunctions)**

Medical devices are being provided for use in this study. In order to fulfil regulatory reporting obligations worldwide, the Investigator is responsible for the detection and documentation of events meeting the definitions of incident or malfunction that occur during the study with such devices.

An incident is any event/malfunction/deterioration in characteristics and/or performance of a device that causes, or has the potential to cause, unexpected or unwanted effects involving the health and safety of participants, users, or other persons. This study focuses on molecular POC devices tests where the medical device itself does not come in contact with the study participant; if any, incident could only be associated with the performance of the respiratory sample collection procedure (procedure-related incident).

All the molecular POC devices investigated are instruments, whose installation will be executed ensuring strict adherence to instructions provided by the manufactures, meeting all requirements as per device manual and site-specific for installing new equipment, and including appropriate safety checks (e.g., electricity). Each device will be operated, cleaned and maintained only by trained staff and according to manufacturer's instructions. This is not an interventional study; therefore, device malfunctions are of limited concern for this study. Nevertheless, should any incident/malfunction arise due to the device itself, inadequate IFU, inappropriate user practice or inappropriate environment in which the device is used or stored, this will be reported by the Investigator to FIND using a dedicated issue/incident log. FIND will inform the manufacturer in case of device malfunction.

NOTE: Incidents fulfilling the definition of an SAE will also follow the processes outlined above.

### **7.1.4 Time Period for Detecting Medical Device Incidents**

Medical device incidents or malfunctions of the device that result in an incident will be detected, documented, and reported during all periods of the study in which the medical device is used.

If the Investigator learns of any incident at any time after a participant has been discharged from the study, and such incident is considered reasonably related to a medical device provided for the study, the Investigator will promptly notify FIND.

Any medical device incident occurring to participant during the study will be documented in accordance with the Investigator's normal clinical practice and on the issue/incident log.

Any medical device incident/malfunction occurring to/detected by user during the study will be documented in accordance with the Investigator's normal practice and on the issue/incident log.

#### **7.1.5 Follow-up of Medical Device Incidents**

All medical device incidents involving an SAE will be followed and reported in the same manner as other SAEs (see Section 7.1.2). This applies to all participants and device users.

The investigator is responsible for ensuring that follow-up includes any supplemental investigations as indicated to elucidate the nature and/or causality of the incident.

New or updated information will be recorded on the originally completed form with all changes signed and dated by the investigator. It is very important that the investigator provides his/her assessment of causality (relationship to the medical device provided by FIND) and describes any corrective or remedial actions taken to prevent recurrence of the incident. A remedial action is any action other than routine maintenance or servicing of a medical device where such action is necessary to prevent recurrence of an incident. This includes any amendment to the device design to prevent recurrence.

#### **7.1.6 Reporting of Medical Device Incidents to FIND**

Medical device incidents will be reported to FIND study team (Clinical Study Manager, Clinical Research Associate, Scientist and Project Manager) within 24 hours after the investigator determines that the event meets the protocol definition of a medical device incident via phone or by email. Where applicable, FIND will promptly inform the manufacturer.

#### **7.1.7 Regulatory Reporting Requirements for Medical Device Incidents**

The investigator will promptly report all incidents occurring with any medical device provided for use in the study in order for FIND to fulfil the legal responsibility to notify appropriate regulatory authorities and other entities about certain safety information relating to medical devices being used in clinical studies.

The investigator, or responsible person according to local requirements (e.g., the head of the medical institution), will comply with the applicable local regulatory requirements relating to the reporting of incidents to the IRB/IEC.

## 8 Statistical Considerations

### 8.1 Sample Size Determination

The sample size was developed in order to be able to obtain an estimate of the expected sensitivity and specificity of the index test based on the analytical data reported by the manufacturers:

- Sensitivity: 97% (Nudge), 98% (GenomEra), 98% (Mirai)
- Specificity: 99%
- Prevalence of COVID-19: 5%

Based on the WHO recommendations, 100 PCR positive will enable us to achieve a power of 80%, with a 95% confidence interval width of 10% under the assumption of a sensitivity value of 97%. A total of 100 confirmed PCR negatives will enable us to achieve an estimate of a specificity of 99% with a two-sided 95% confidence interval width of 6% and a power of 80%. With an estimated disease prevalence of 5% and a prevalence power of 80%, recruiting 100 confirmed positives will be the limiting factor, and 2171 participants are needed to be screened to reach this number.

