
Sample Size
	
Enrolment will target to reach 100 specimens with detectable SARS-CoV-2 RNA levels (by RT-PCR) and 100 specimens with no detectable SARS-CoV-2 RNA levels, as recommended by the WHO EUL “Instructions and requirements for Emergency Use Listing (EUL) Submission: In vitro diagnostics detecting SARS-CoV-2 nucleic acid or antigen”.
 
Based on the assumption that the sensitivity of the index tests will be at least 97%, 100 PCR positive will enable us to achieve an estimate with two-sided 95% confidence interval of 10%, with power of 80%. A total of 100 confirmed PCR negatives will enable us to achieve an estimate of a specificity of 99% with a two-sided 95% confidence interval width of 6% and a power of 80%. With an estimated disease prevalence of 5% and a prevalence power of 80%, recruiting 100 confirmed positives will be the limiting factor, and 2171 participants are needed to be screened to reach this number.
 
Should the COVID-19 prevalence fall below 1% for more than continuous 2 weeks, enrolment may be paused and resumed when the epidemic situation changes. Should the epidemic situation not change, introduction of supplementing approaches will be considered.

Eligibility criteria
	
Participants/specimens are eligible to be included in the study only if all the following Inclusion criteria apply:
 
 
• Adult individuals (≥18 years of age) with symptoms suggesting plausible COVID-19 infection (as per WHO or national clinical case definitions)
 
• Individuals who have voluntarily given written consent to participate in this study or who have given their written consent for their specimen to be used for future research studies
 
• Individuals able to provide the specimens required for the study
 
 
Participants are not eligible to be included in the study if any of the following Exclusion Criteria apply:
 
 
• Individuals on oxygen therapy
 
• Individuals with recent history of excessive nose bleeds
 
• Individuals with hemodynamic instability as determined by their treating physician
 
• Individuals already enrolled in other clinical studies, where similar respiratory specimens are collected on the same day.
 

Study duration
	
The study will last approximately 6-9 months.

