#### General Methodology

Point estimates of sensitivity and specificity, with 95% confidence intervals based on Wilson's score method, will be calculated following the definitions below:

**Table 5:** Case predictions

		Reference standard classification		
		Positive	Negative	Total
Case prediction	Predicted positive	a	b	(a + b)
	Predicted negative	c	d	(c + d)
	Total	(a + c)	(b + d)	(a + b + c + d)

**Table 6:** Sensitivity and Specificity

a = True Positives	Sensitivity = $a / (a + c)$
b = False Positives	Specificity = $d / (b + d)$
c = False Negatives	
d = True Negatives	

The analyses of accuracy will be performed on the PP population for the analysis of the Endpoint 1.1, and will be stratified by the subgroups specified below for the analysis of the Endpoint 2.1:

- Sex (Men/Women)
- Days after symptom onset (1-3 days, 4-7 days, >7 days)
- Reference PCR Ct value (Ct < 18, 18 < Ct <= 25, 25 < Ct <= 33, Ct > 33)
- By COVID-19 vaccination status (no vaccination, one dose vaccination, multi-dose vaccination) as per information collected from participants
- By presence of previous SARS-CoV-2 infection(s) as per information collected from participants
- By SARS-CoV-2 genetic variant causing infection

The sum of usability scores will be calculated for the analysis of the Endpoint 2.2  
Further details of each analysis will be described in the SAP.

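### At the minimum of 100 PCR negatives, a specificity interval no wider than 6% has probability 73.6%, not the stated 80%; the companion sensitivity statement is conservative

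*Protocol*

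**What the plan says.** Protocol section 8.1 (Sample Size Determination) assumes "Sensitivity: 97% (Nudge), 98% (GenomEra), 98% (Mirai"%), "Specificity: 99"% and a prevalence of 5%. It then makes three numerical statements:

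- **Sensitivity:** "100 PCR positive will enable us to achieve a power of 80%, with a 95% confidence interval width of 10"%, at an assumed sensitivity of 97%.
- **Specificity:** at an assumed 99%, the planned 100 negatives are said to give "a two-sided 95% confidence interval width of 6% and a power of 80"%.
- **Recruitment:** "recruiting 100 confirmed positives will be the limiting factor, and 2171 participants are needed to be screened to reach this number", at 5% prevalence and a prevalence power of 80%.

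The Sample Size row of the Protocol Synopsis repeats all three. Its sensitivity sentence omits the word 'width': "100 PCR positive will enable us to achieve an estimate with two-sided 95% confidence interval of 10%, with power of 80"%. The synopsis attributes the target of 100 positive and 100 negative specimens to a WHO recommendation.

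The primary endpoint (section 2, Table 1) is a point estimate of sensitivity and of specificity with 95% confidence intervals. Section 8.3, General Methodology, fixes the interval: "with 95% confidence intervals based on Wilson's score method". Section 3.3 treats the positive and negative counts as minimums whose attainment ends the study.

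**The concern.** Power normally belongs to a test against a stated value. This protocol states no null value, performance threshold or hypothesis, so the two 80% figures attached to interval widths need another meaning. The only natural one is the probability, over repeated samples, that the 95% interval comes out no wider than stated. On that reading, the specificity figure does not follow from the protocol's own inputs and method.

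These sentences tell a reader what precision the minimum sample delivers for the primary endpoint. One stated probability is too high and the other too low, although both carry the same 80% label. The specificity figure matters most if negatives stay close to 100. That could happen if the supplementing approaches in section 3.1 are used, since section 4.3 allows biobank specimens to be selected by previous RT-PCR result.

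**Working it through.** **Inputs.** n = 100 negatives, specificity 99%, width 6%; n = 100 positives, sensitivity 97%, width 10%; stated probability 80% for each; prevalence 5% (all section 8.1). The interval is Wilson, two-sided 95%, z = 1.96 (section 8.3).

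**Step 1: reproduce the recruitment figure.** Find the smallest N for which the number of positives, binomial with probability 0.05, reaches 100 with probability 80%. By normal approximation at N = 2171, the expected number of positives is 0.05 × 2171 = 108.55 and the standard deviation is √(2171 × 0.05 × 0.95) = 10.155. Then (108.55 − 100)/10.155 = 0.842, which gives a probability of 80.0%. The figure of 2171 reproduces. The exact binomial calculation gives 2162, and 81.3% at 2171.

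**Step 2: Wilson width.** For x correct results out of n:

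width = [2z/(n + z²)] × √[x(n − x)/n + z²/4]

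At n = 100:

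| Errors | Correct | Width (points) |
|---|---|---|
| 0 | 100 | 3.70 |
| 1 | 99 | 5.27 |
| 2 | 98 | 6.45 |
| 4 | 96 | 8.27 |
| 6 | 94 | 9.70 |
| 7 | 93 | 10.32 |

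For example, at x = 98: (3.92/103.84) × √(1.96 + 0.96) = 0.0645.

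**Step 3: specificity.** A width of at most 6% requires at most 1 false positive. With a false-positive probability of 0.01:

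- P(0) = 0.99^100 = 0.3660
- P(1) = 100 × 0.01 × 0.99^99 = 0.3697
- P(at most 1) = 0.7358, or **73.6%**

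Adding P(2) = 0.1849 gives 92.1% for a width of at most 6.5%. The probability jumps from 73.6% to 92.1% with no value near 80% between them.

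**Step 4: other readings of the specificity figure.**

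| Reading | Probability |
|---|---|
| Clopper-Pearson interval | 73.6% |
| Wald or Jeffreys interval | 92.1% |
| Agresti-Coull interval | 36.6% |
| 6% taken as a half-width | 100% |
| Exact test of 99% against 93%, one-sided 0.025 / 0.05 | 73.6% / 92.1% |

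None gives 80%. Under Wilson, the smallest number of negatives that meets the claim is 108, where two false positives give a width of 5.99 points. Under Clopper-Pearson it is 114.

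**Step 5: sensitivity.** A width of at most 10% allows up to 6 false negatives. With a false-negative probability of 0.03, P(at most 6) = 0.9688, or **96.9%**, against the stated 80%. Clopper-Pearson gives 91.9%. The Wilson width reached with at least 80% probability is 8.3 points (at most 4 false negatives, probability 81.8%).

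**Step 6: negatives expected under consecutive enrolment.** Stopping at the 100th positive at 5% prevalence expects 100/0.05 = 2000 participants, hence 2000 − 100 = 1900 negatives. At 1881/1900 (99%) the Wilson interval runs from 98.44% to 99.36%, a width of 0.92 points. If all 2171 are enrolled, 0.95 × 2171 ≈ 2062 negatives are expected, and 2041/2062 gives a width of 0.88 points.

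**The case against.** The strongest reply is that the shortfall is small and may never arise. The mean Wilson width at 100 negatives and 99% specificity is 5.1 points. Two false positives give 6.45, which rounds to 6, and that width is met with 92% probability. Positives are the limiting factor, and the per-protocol population in section 8.2 has no cap on negatives, so a purely prospective study would far exceed the promised precision. The 100 + 100 target is taken from WHO, so the precision sentences describe that size and did not generate it. All of this stands. It limits the weight of the point but does not make 80% correct for the 100 negatives to which the sentence refers.

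A reader might infer several stronger things that the protocol does not support:

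- *That the sensitivity claim also fails.* It does not. At the stated 97%, which is the lowest of the three device values, the promised precision is met with more than the stated probability. Lower true sensitivities would give less, but section 8.1 conditions explicitly on 97%.
- *That some 2000 negatives contradict a target of 100.* An excess of negatives follows from positives being limiting and from the counts being minimums (section 3.3). The 6% describes precision at the minimum and does not forecast the final interval.
- *That about 2060 negatives per device will be analysed.* That number belongs to the 80%-assurance figure of 2171. Stopping at the 100th positive expects about 1900, and the enrichment or biobank routes in section 3.1 would change the ratio.
- *That 2171 is wrong or too small.* It reproduces. The protocol gives no rate of invalid results from which to calculate a loss, and the end of the study is defined by counts reached, so 2171 is not a cap.

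**Conclusion.** The point holds in a narrow form. With 100 negatives, a true specificity of 99% and Wilson's interval, the probability of a width of at most 6% is 73.6%, which is 6.4 percentage points below the stated 80%. The conclusion rests on reading 'power' as the probability of attaining the width, the only reading that fits a study without a hypothesis; none of the alternatives tried gives 80% either. The sensitivity sentence is conservative, at about 97% against 80%. This is a correction to a stated figure and to a term. It gives no ground for changing the sample size, the 2171, the endpoint or the analysis.

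**What to change.** In section 8.1 and the synopsis:

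1. Replace 'power', where it is attached to an interval width, with 'probability that the Wilson 95% confidence interval is no wider than'. Write 'width' in the synopsis sensitivity sentence too.
2. Restate the figures at the minimum counts:
   - 100 negatives at 99%: width at most 6% with 74% probability (at most 6.5% with 92%).
   - 100 positives at 97%: width at most 10% with 97% probability (at most 8.3% with 82%).
3. Add that the specificity figures describe the minimum of 100 negatives. Under consecutive enrolment at 5% prevalence, with all valid results analysed, about 1900 negatives are expected when the 100th positive is reached (about 2060 if all 2171 are enrolled), and specificity would then be estimated with a width of about 1 point. Say that enrichment or biobank supplementation would alter this.

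The cost is wording only. No participants are added and 2171 stays. One stated figure becomes slightly less favourable.
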